Phase 4: Control phase initiation. Sites will be trained in the study protocol, recruitment procedure, consent process, and how to use the decision support tool recruitment modules. Recruitment of control patient subjects will begin following this training. Data quality assessment procedures and baseline standardized patient interviews with care manager provider subjects will also occur in this phase.

Phase 5: Follow-up outcome assessments. Follow-up interviewer training will begin prior to the initiation of this phase. The 3-, 6- and 12-month, blinded follow-up interviews will begin and continue ongoing throughout this phase.

Phase 6: Intervention phase initiation. Recruitment of control patient subjects will end at each site based upon the wave they are assigned in the stepped wedge design. The UW intervention study team members will conduct a one-day intervention training workshop at each site at this time. Following this training, each site begins recruitment of intervention patient subjects and their care manager subjects begin charting notes in the decision support tool and have regular supervision with the UW study team. Intervention feedback and coaching will occur during this phase. Standardized patient sessions continue during this phase. Data quality assessment procedures will also continue at each site in this phase. All provider subjects will be asked to complete another organizational survey, after this phase is completed.

Phase 7: Final study procedures. Final data cleaning and analyses will be conducted in this phase. Manuscript preparation and the end of study policy summit will occur in this phase. The UW study team will coordinate with the American College of Surgeons' Committee on Trauma, as well as other stakeholders to hold a policy summit.

C. Site Eligibility and Recruitment

Over the course of the start-up phase, the TSOS study team has recruited the 24 trauma center sites that will

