After the one-day workshop training, Drs. [name] and [name] will initiate between 1-4 care management supervisory calls each month (e.g., weekly calls) for the duration of the intervention period at each site. Utilizing the computerized decision support tool, the care managers will present cases to the supervisory team. These regular meetings may range between approximately 15 minutes and 2 hours depending on the number of patient subjects and symptomatic intensity of caseloads. These sessions will include coaching in concern elicitation, CBT and MI techniques, as well as problem-solving surrounding organizational obstacles to screening and intervention implementation for PTSD and related comorbidity. These calls will also include coaching on evidence-based medication prescription for PTSD and comorbidity. The computerized decision support tool will also be used to assess fidelity to specific care management, behavioral therapy, and pharmacotherapy elements of the clinical treatment protocol. The care managers will be able to contact Drs. [name] and [name] by phone if specific questions regarding patients arise; of particular note, Drs. [name] and [name], will provide written feedback on questions via the staffing notes function in the decision support tool. With care manager subject permission, elements of any training/supervision procedures may be audio-recorded for educational or fidelity purposes.

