The study team will use ANCOVA/mixed effects regression models to test the hypotheses. The investigative group has extensive experience with these analytic approaches in the analyses of longitudinal data after injury. These analytic approaches allow for the modeling of longitudinal data on patients, nested within trauma center sites (see also sample size and power discussion below for a more in-depth discussion of clustering). An important potential advantage of using longitudinal mixed models is the ability to use partial data on those of subjects with missing data, and therefore potentially ameliorate selection bias due to drop-out. In addition, mixed models naturally structure patient and center heterogeneity specifically allowing for random effects such as individual intercepts and slopes on time. Longitudinal regression models also allow the use of baseline covariates that may be prognostic or reflective of the study design.

Exploratory analyses will assess the impact of the intervention on primary and secondary outcomes for patients with and without pre-injury chronic medical conditions and with and without TBI. Exploratory analyses will also assess for significant reductions in suicidal ideation, pain and drug use problems in intervention patients when compared to control patients. The study team will again use ANCOVA/mixed effects regression for these exploratory analyses.²⁹⁴⁻²⁹⁷ In order to assess for potential selection bias across clusters, demographic characteristics (e.g., gender, ethnicity, insurance status) will also be tested as main effects and interactions with treatment status.

3. Stepped wedge cluster randomized design

Variability in multiple trauma center characteristics can impact rates of recruitment (e.g., admission volumes, EHR capacity), rates of PTSD (e.g., percentages of patients with violent injury admissions, intensive care unit admission rates), and the ability to follow patients longitudinally (e.g., patient demographic characteristics such as being homeless, clinical characteristics such as substance use problems). The study team initially considered using a stratified randomization procedure; however given the potential variability in multiple trauma center characteristics the study team will use a stepped wedge cluster randomized design for the UH3

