protocol. The stepped wedge design randomizes level I trauma center sites to sequentially initiate the intervention, thus allowing within site pre-, post- intervention comparisons, as well as between site comparisons. An additional advantage of the stepped wedge design for the UH3 protocol is that it would be impractical to roll out the entire intervention at 24 sites simultaneously. Finally, from an implementation science perspective there is an advantage to having the intervention ongoing at the end of the study at every site, should the intervention demonstrate a significant impact on PTSD and comorbidity. Given that there is little threat of contamination at each site across intervention and control patients and that the UH3 can accommodate the increased potential length of active recruitment and follow-up, the stepped wedge design appears to be an optimal choice for the UH3 protocol. In the proposed UH3 protocol stepped wedge design, all 24 participating level I trauma centers are randomly assigned to 1 of four waves. Each wave is assigned a specific proportion of control and intervention patient recruitment. Wave 1 recruits 8 control and 32 intervention patients, wave 2 recruits 16 control and 24 intervention, wave 3 recruits 24 control and 16 intervention and wave 4 recruits 32 control and 8 intervention patients. Interventions are initiated in the second six months of the UH3. The proposed stepped wedge design is outlined in the figure below.

Figure 16. Stepped Wedge Cluster Randomized Design

The stepped wedge regression model will adapt the functional form given below, and uses a timedependent variable to code treatment status for cluster *k* at calendar time *t*, denoted as condition_{kt.} For the stepped wedge study design there are now two key time scales: Period, which denotes the study period measured relative to the calendar time when the overall study begins; and Follow-up time which is a patientspecific time scale relative to when they enrolled in the study. In this model mean outcomes may have a temporal trend in calendar time and this will be captured by modeling "Period", while the primary outcome will still be the 12-month patient outcome denoted by Y_{ijkt} where i=4.

A) The primary analysis regression model will adapt the functional form given below:

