 $Y_{4jkt} = \beta_0 + \beta_1^* \text{Period}_{4jk1} + \beta_2^* \text{Period}_{4jk2} + \beta_3^* \text{Period}_{4jk3} + \beta_4^* \text{Period}_{4jk4} + \beta_5^* Y_{1jkt} + \beta_6^* \text{condition}_{kt} + \text{Mean model}$

Trauma center random effect and error

 $b_{k,0} + e_{4jkt}$

For this analysis the null hypothesis of no intervention effect is captured by H_0 : $\beta_6=0$, and the primary statistical test will be a Wald test of this null hypothesis.

B) A secondary analysis will explore the potential for treatment effect heterogeneity at the center level through inclusion of an additional random effect that permits cluster-specific variability in the intervention impact, captured by a random coefficient on the time-varying condition covariate:

 $Y_{4jkt} = \beta_0 + \beta_1 * \text{Period}_{4jk1} + \beta_2 * \text{Period}_{4jk2} + \beta_3 * \text{Period}_{4jk3} + \beta_4 * \text{Period}_{4jk4} + \beta_5 * Y_{1jkt} + \beta_6 * \text{condition}_{kt} + \text{Mean model}$

 $b_{k,0} + b_{k,1}$ *condition_{kt} + e_{4jkt}

Trauma center random intercept, slope, and error

The key difference for this model is that the intervention effect at trauma center k would be allowed to vary across centers and would involve the overall average intervention effect and a center-specific random intervention effect: β_6 + $b_{k,1}$. For this analysis the null hypothesis of a null average intervention effect is still captured by H₀: β_6 =0, and the primary test will be a Wald test of this null hypothesis, but now using an additional random intervention effect together with a standard random trauma center effect (random intercept).

C) A secondary analysis will evaluate the impact of intervention at all of the longitudinal follow-up times by including additional outcome measures and associated follow-up time variables, and interactions between follow-up time and intervention:

$$\begin{split} Y_{ijkt} &= \beta_0 + \beta_1 * \text{Period}_{ijk1} + \beta_2 * \text{Period}_{ijk2} + \beta_3 * \text{Period}_{ijk3} + \beta_4 * \text{Period}_{ijk4} + \beta_5 * \text{Followup}_{2jkt} + \beta_6 * \text{Followup}_{3jkt} + \\ \beta_7 * \text{Followup}_{4jkt} + \beta_8 * \text{condition}_{kt} + \beta_9 * \text{Followup}_{2jkt} * \text{condition}_{kt} + \beta_{10} * \text{Followup}_{3jkt} * \text{condition}_{kt} + \\ \beta_{11} * \text{Followup}_{4jkt} * \text{condition}_{kt} + \\ \end{split}$$

Mean model

a _{jk,0} + a _{jk,1} *Followup _{ijkt} +	Patient random effects

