$b_{k,0} + b_{k,1}$ *condition _{kt} + e_{ijkt}	Trauma center random effects and error

Y_{ijkt} denotes patient outcome at follow up time i (i=1,2,3,4) (baseline, 3m, 6m, 12m)

for patient j ($j=1,2,...,n_k$)

at trauma center k (k=1,2,...,24)

enrolled in time period t (t=0,1,2,3,4)

For secondary analysis using the repeated measurements from each subject there are two key hypotheses to test. First, the 12-month intervention effect would now be captured by the intervention-by-time interaction specific to the 12-month assessment time: H_0 : β_{11} =0; and evaluation of the intervention effect under this model evaluates any impact of using the partially complete longitudinal data for all subjects to estimate the 12-month intervention effect. This analysis provides a sensitivity analysis evaluating the impact of missing 12-month data for subjects who do have partial follow-up data (e.g. 3 month, 6 month data). A second exploratory hypothesis would be the global null of no intervention effect at all follow-up times, and this would be captured by the multivariate null hypothesis: H_0 : $\beta_8 = \beta_9 = \beta_{10} = \beta_{11} = 0$; and evaluated using a multivariate Wald test. Under this hypothesis the intervention and control means within a given period would be equivalent for all patient follow-up times.

The primary analysis is a single hypothesis test based on Model (A) and will use alpha=0.05. All other statistical tests are conducted to evaluate the sensitivity of the primary analysis to either heterogeneity or missing data, and therefore multiple comparison corrections are not used for these secondary analyses.

Subject Attrition: Some attrition is expected in the study sample due to the research context and the population under study (i.e., low income, ethnoculturally diverse, injured trauma survivors). Prior studies by the

investigative group have consistently achieved follow-up completion rates \geq 75-80% at 12 months post-injury with this population. Estimates derived from these rates are incorporated into the descriptions of subject flow and power analyses.

4. Sample size and power

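### No planned model has a term for time since a site's workshop; at the planning values Model A's β6 puts about 0.71 of its weight on the first intervention step, which holds 40% of treated patients

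*Combined protocol and SAP*

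**What the plan says.** The models are in the Statistical Analysis Plan, section 3 (Stepped wedge cluster randomized design). The regression "uses a timedependent variable to code treatment status for cluster" k at calendar time t. The section names two time scales, calendar period and patient follow-up time. On the first it says that "mean outcomes may have a temporal trend in calendar time and this will be captured by modeling" the Period terms.

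- **Model A (primary):** 12-month score on Period indicators, the baseline score, condition (β6) and a random site intercept, with a Wald test of β6 = 0 at alpha 0.05.
- **Model B:** its purpose is to "explore the potential for treatment effect heterogeneity at the center level through inclusion of an additional random effect". That effect is constant over time within a site.
- **Model C:** all visits, with condition-by-follow-up terms. Here "the 12-month intervention effect would now be captured by the intervention-by-time interaction specific to the 12-month assessment time", β11. On its purpose the plan says: "This analysis provides a sensitivity analysis evaluating the impact of missing 12-month data for subjects who do have partial follow-up data".

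On delivery, Phase 6 of the Study Phases section describes a one-day workshop, then: "Following this training, each site begins recruitment of intervention patient subjects". The Stepped Collaborative Care Intervention Condition section says the supervisors "will initiate between 1-4 care management supervisory calls each month (e.g., weekly calls) for the duration of the intervention period at each site".

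**The concern.** Sites start treating patients straight after one day of training and are then coached for the rest of the intervention period. The effect could grow as care managers gain experience, or fade. The documents take no position.

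If the effect depends on time since the workshop, a single on/off coefficient in a stepped wedge model does not average it over treated patients. It forms a weighted sum whose weights come from the layout and the ICC, and some weights can be negative. β6 would then be too low for the average treated patient if the effect rises with experience, and too high if it wanes. The trial is meant to inform national trauma center policy, so the size of the effect matters as well as its sign.

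Models B and C do not fill the gap. Model B has no exposure-time index. Model C gives a second 12-month estimate, β11, but it has no Period-by-follow-up term, so a calendar trend in change from baseline enters β11. A difference between β6 and β11 would therefore mix exposure time, calendar trend and missing data.

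**Working it through.** **Inputs.** From section 3: 24 sites, four waves, five periods (t = 0 to 4), and control:intervention splits of 8:32, 16:24, 24:16 and 32:8. From Table 11: 30 completers per site at 12 months (6 per site-period), ICC 0.02, autocorrelation 0.7, power 80%. Assumed: 6 sites per wave, equal periods and two-sided alpha. Figure 16 is not shown, but splits in steps of 8 fit equal periods.

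**1. Reproduce the plan's figure.** Per site, the covariance of the five period means is V = ((1 - ICC)/6)·I + ICC·J. The minimum detectable effect is (1.96 + 0.84) × SE(β6), where SE includes the factor √(1 - 0.7²) = 0.714. At ICC 0.02, SE = 0.1133 × 0.714 = 0.0809 and the result is 0.227. At ICC 0.005, 0.010, 0.020 and 0.030 it is 0.216, 0.220, 0.227 and 0.231, which matches all four Table 10 values.

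**2. Weights of β6.** Take the β6 row of (X'V⁻¹X)⁻¹X'V⁻¹. At ICC 0.02, by wave and period:

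| Wave | t=0 | 1 | 2 | 3 | 4 |
|---|---|---|---|---|---|
| 1 | -0.054 | 0.300 | 0.182 | 0.064 | -0.054 |
| 2 | -0.018 | -0.136 | 0.218 | 0.100 | -0.018 |
| 3 | 0.018 | -0.100 | -0.218 | 0.136 | 0.018 |
| 4 | 0.054 | -0.064 | -0.182 | -0.300 | 0.054 |

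Add the treated cells by step since the switch:

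- Step 1: 0.300 + 0.218 + 0.136 + 0.054 = 0.707 (before rounding)
- Step 2: 0.182 + 0.100 + 0.018 = 0.300
- Step 3: 0.064 - 0.018 = 0.046
- Step 4: -0.054

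Treated patients by step are 192, 144, 96 and 48 of 480, that is 0.40, 0.30, 0.20 and 0.10.

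**3. Sensitivity of the step-1 weight.**

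- ICC 0.005, 0.0083 (the team's own estimate), 0.03: 0.63, 0.65, 0.74.
- Baseline adjustment shrinking only the residual variance (conditional ICC 0.02/(0.02 + 0.98 × 0.51) = 0.0385): 0.77.
- Switch dates staggered by up to half a period within waves: 0.62 to 0.70, on about 39% of treated patients.
- Uneven recruitment. Section 3 itself notes: "Variability in multiple trauma center characteristics can impact rates of recruitment". Over 2000 layouts (assumed 15 to 45 completers per site, uneven period shares), the 95% range is 0.59 to 0.81.

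**4. What this does to the estimate.** The curves below are assumptions, as relative effects at steps 1 to 4. The gap in the last column assumes a patient average of 0.34 SD, the effect quoted in section 4.

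| Curve | β6 | Patient average | Ratio (uneven-recruitment range) | Gap (SD) |
|---|---|---|---|---|
| 0.75, 0.83, 0.92, 1 | 0.769 | 0.833 | 92% (91-94) | 0.026 |
| 0.5, 1, 1, 1 | 0.646 | 0.800 | 81% (76-86) | 0.065 |
| 1, 0.75, 0.5, 0.25 | 0.942 | 0.750 | 126% (118-133) | 0.087 |
| 0.25, 0.5, 0.75, 1 (extreme) | 0.308 | 0.500 | 62% (55-69) | 0.131 |

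**5. Model C.** With complete data, β11 is the treated-minus-control difference in mean change from baseline to 12 months, so its step weights are the patient shares. With 25% of 12-month scores missing at random, the step-1 weight was 0.36 to 0.41. The mean enrolment period is (10 + 9 + 7 + 4)/10 = 3.0 for treated patients and (0 + 1 + 3 + 6)/10 = 1.0 for controls. A drift d per period in 12-month but not baseline scores therefore shifts β11 by 2d. With an assumed d = 0.05 SD (0.75 PTSD Checklist points at SD 15), β11 moves 0.10 SD (1.5 points) with no exposure effect. Drifts of 0.013, 0.033 and 0.044 SD give the first three gaps in the table. A linear drift moves β6 by 0, because Model A has Period terms.

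**6. Precision of an exposure-step model.** At ICC 0.02, its patient-weighted average has SE 0.088. Its difference from β6 has SE √(0.0881² - 0.0809²) ≈ 0.035, so the 95% interval is about ±0.07 SD (±1 point). Over ICC 0.005 to 0.03 that SE is 0.025 to 0.040. The chance of detecting the first three gaps is 12%, 47% and 71%.

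**The case against.** The plan is not in error if the effect is constant: Model A is then correctly specified and β6 is unbiased. The documents do not name the patient-weighted average as the target, every curve above is assumed, and the mild case moves β6 by only 0.026 SD. The plan also works to keep delivery uniform and to measure it. The same central team supervises all sites, the decision support tool tracks adherence, and standardized patient interviews are repeated after training and at the end of recruitment (Fidelity Assessments). The added model would rarely detect a mild gap, its step-4 estimate rests on wave 1 alone (SE about 0.18), and it assumes one curve for all waves. Finally, 0.71 is a Model A figure. Model B's weights depend on a random-effect variance the documents do not give, and β6 in Model C is a follow-up coefficient.

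Most of this stands as a limit on how strongly the point can be put: it is a robustness check, and real distortion in this trial is not shown. It does not remove the point. Fidelity monitoring is not an outcome analysis by exposure step. The excess weight on step 1 held under every ICC, staggering and recruitment assumption tried.

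**Conclusion.** The concern holds, as an improvement worth considering. No planned model allows for time since the workshop. At the planning values, Model A's β6 puts 0.71 of its weight on the step that holds 40% of treated patients, and a net weight of about zero (0.046 - 0.054 = -0.008) on steps 3 and 4, which hold 30%. The weights rest on equal waves and periods and ICC 0.02; the step-1 weight was 0.59 to 0.81 over the variations tried. Whether β6 is distorted depends on an exposure effect that the documents do not address: from 8% low under a mild rise to 26% high under linear waning, with an extreme ramp 38% low. The level of the primary test is unaffected when no step has an effect.

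**What to change.** Keep the Model A Wald test as the sole primary test at alpha 0.05. Beside Models B and C, pre-specify one sensitivity model that keeps Model A's Period terms, baseline covariate and random site intercept, and replaces the condition term with indicators for step 1 to 4 since the site's workshop. Report:

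- the average of the step effects, weighted by realised patient shares (planned 0.4, 0.3, 0.2, 0.1), with a 95% confidence interval, next to β6;
- the difference between the two, with its 95% confidence interval, and the size of gap that interval excludes.

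Set no pass/fail rule. State in advance that a non-significant difference does not establish a constant effect, and that a gap between β6 and β11 will not be read as evidence on exposure time.

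The cost is one extra model, with no new data and no change to alpha or sample size. The downsides are the lower precision, the low power for small gaps and the single assumed exposure curve noted above. The model bounds the gap; it cannot rule one out.

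### Model C adjusts for enrolment period only as a main effect, so its 12-month effect is open to calendar drift in recovery and cannot isolate the impact of missing 12-month data

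*Combined protocol and SAP*

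**What the plan says.** Statistical Analysis Plan section 3 (Stepped wedge cluster randomized design) says that "mean outcomes may have a temporal trend in calendar time and this will be captured by modeling" Period. Models A and B regress the 12-month score on Period indicators, the baseline score and condition.

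Model C extends this by "including additional outcome measures and associated follow-up time variables, and interactions between follow-up time and intervention". Its outcome index runs over baseline, 3, 6 and 12 months. The fixed effects are Period (β1–β4), Followup (β5–β7), condition (β8) and Followup-by-condition (β9–β11). There is no Period-by-Followup term. The key below the model describes a patient as "enrolled in time period t (t=0,1,2,3,4").

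Three statements then rest on Model C:

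- The 12-month test: "First, the 12-month intervention effect would now be captured by the intervention-by-time interaction specific to the 12-month assessment time", that is, β11 = 0.
- Its purpose: "This analysis provides a sensitivity analysis evaluating the impact of missing 12-month data for subjects who do have partial follow-up data".
- The meaning of the global null β8 = β9 = β10 = β11 = 0: "Under this hypothesis the intervention and control means within a given period would be equivalent for all patient follow-up times".

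Model C is not primary: "The primary analysis is a single hypothesis test based on Model (A"). Of the rest, the section says: "All other statistical tests are conducted to evaluate the sensitivity of the primary analysis to either heterogeneity or missing data".

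**The concern.** Because baseline is an outcome row, β11 is a difference in change from baseline. An enrolment-period effect that enters identically in all four of a patient's rows drops out of that change. Model C therefore allows for a calendar trend in the level of scores but not for one in recovery. In a stepped wedge, intervention patients enrol later by design, so such a trend is confounded with condition.

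What is at stake is the reading of the sensitivity analysis. If Models A and C disagree, the plan would attribute this to missing 12-month data, when drift in recovery could produce the same gap with nothing missing. Drift could also mask a real missing-data difference. The 3- and 6-month effects (β9, β10) have the same weakness, and section 2 of the plan wants change at those times for the primary and all secondary outcomes.

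**Working it through.** **Inputs from the documents.** 24 sites in four waves (6 per wave, assuming equal waves); 40 patients per site; control/intervention splits of 8/32, 16/24, 24/16 and 32/8 (section 3). This gives five enrolment periods with 8 patients per site-period. Table 11 gives 25% attrition at 12 months, ICC 0.02, SD 15 and autocorrelation 0.7.

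**The plan's own figure.** Stepped-wedge variance with 6 completers per site-period and total variance 1, multiplied by (1 − 0.7²) for baseline adjustment; detectable effect = (1.96 + 0.84) × SE. Results are 0.2161, 0.2203, 0.2267 and 0.2311 at ICC 0.005, 0.010, 0.020 and 0.030. Table 10 gives 0.216, 0.220, 0.227 and 0.231, so the layout is the one the plan used. The Model A SE at ICC 0.02 is 0.2267 / 2.80 ≈ 0.08 SD.

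**Confounding of condition with period.** Waves under control in periods 0–4: 4, 3, 2, 1, 0. Under intervention: 0, 1, 2, 3, 4. Each condition has 10 wave-periods × 6 sites × 8 patients = 480 patients.

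- Control mean period = (0×4 + 1×3 + 2×2 + 3×1)/10 = 1.0
- Intervention mean period = (1×1 + 2×2 + 3×3 + 4×4)/10 = 3.0

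**Bias under no true effect.** Site, patient-intercept and Period terms all cancel from change.

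- *Drift shared by baseline and follow-up:* bias 0, rejection 5%. A linear trend by assessment date also gives bias 0, because it splits into Period plus Followup main effects.
- *Linear follow-up-only drift g per period:* bias = g × (3.0 − 1.0) = 2g.
- *One-off follow-up-only shift d:* the share of patients enrolled after the shift differs between conditions by 10/10 − 6/10 = 0.4, 9/10 − 3/10 = 0.6, 7/10 − 1/10 = 0.6 or 4/10 − 0 = 0.4, for a shift at period 1, 2, 3 or 4. The bias is 0.4d to 0.6d.

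**Rejection rates.** Expected generalised least squares estimates and SEs were computed on this layout, with assumed monotone missingness of 15/20/25% at 3/6/12 months. Drift sizes are assumptions.

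| Follow-up-only drift per period | Correlation | Patient slope variance (SD²/yr²) | Bias in β11 (SD) | Rejection at 5% |
|---|---|---|---|---|
| 0.02 SD | 0.7 | 0 | 0.04 | 11% (7–11% over the range) |
| 0.05 SD | 0.7 | 0 | 0.10 | 43% |
| 0.05 SD | 0.5 | 0 | 0.10 | 29% |
| 0.05 SD | 0.7 | 0.5 | 0.10 | 26% |
| 0.05 SD | 0.5 | 0.5 | 0.10 | 20% |

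Check on the second row: the SE is 0.056, so the standardised bias is 0.10/0.056 = 1.79, and Φ(1.79 − 1.96) ≈ 0.43. A one-off shift of 0.05 SD gives 6–8%.

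**With no missing data.** The variance of change is 2 × (1 − 0.7) = 0.6, so SE = √(0.6 × 2/480) = 0.05. The bias is still 0.10 and rejection is 52%. Model A gives bias 0 under the same drift. The two models therefore differ without any missing-data effect. The factor of 2 did not change under any missingness pattern tried.

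**Global null.** At g = 0.05 SD, within-period means are equal at every follow-up time by construction. The expected β8–β11 are nevertheless −0.064, 0.10, 0.10 and 0.10, and the 4-df test rejects 41% of the time (22–41% over the same range).

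**Assessment-date reading of Period.** Model C writes Period with the follow-up subscript, which could mean calendar date of assessment. Assuming 6-month periods with extra indicators for later dates, the bias under follow-up-only drift is about 1.0g at correlation 0.7 (11% rejection at g = 0.05) and as low as 0.4g under other codings. It is reduced but not removed.

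**The case against.** The strongest reply is that only a secondary model is affected. Model A is the single primary test, the plan gives Model C no formal alpha, and the drift sizes are invented. The 43% needs monotone drift of 0.75 points per period (3 points over four periods) with baseline flat and no patient slope, yet Model C includes a patient slope. The calendar trends one would think of first, shared or linear in assessment date, do no harm. On mean squared error, the model as written is better when (2g)² < 0.079² − 0.056², that is, for g below about 0.028 SD (about 0.038 with slope variance 0.5). Adding the interaction also leaves other differences from Model A: Model C has a site-level random condition effect and a free baseline contrast β8, whereas A conditions on baseline. Finally, the plan says the functional form will be adapted.

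Most of this stands as a limit on the size of the problem. It does not rescue the interpretation. A model meant to test sensitivity to missing data should not depend on an extra no-drift assumption that Model A does not make, and the smaller SE is valid only if that assumption is true. The documents also give reasons why baseline and follow-up need not drift alike: baseline is truncated at a PTSD Checklist score of 35 and collected by site recruiters, who receive feedback on screen-in rates, while follow-up is collected by separate blinded interviewers. The random condition effect did not change β11 in the calculations. Planned adaptation of the form does not supply the missing term.

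**Conclusion.** The concern holds. On the plan's definition of Period, β11 is not adjusted for calendar drift in change from baseline. It is biased by twice the per-period drift when that drift is linear and confined to follow-up, and by 0.4 to 0.6 of a one-off shift. The stated meaning of the global null also fails under such drift. The algebra needs no assumption beyond the planned allocation and enrolment-period coding. The rejection rates (11% at 0.02 SD per period, 20–43% at 0.05 SD) depend on assumed drift, correlation and slope. If change from baseline does not drift, β11 is unbiased on this point. The primary test and the stated power are unaffected. This should be fixed before analysis, because otherwise a disagreement between Models A and C has no clear reading.

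**What to change.** State that Period in Model C is the enrolment period, and add Period-by-Followup interactions (4 × 3 = 12 parameters). Read the 3-, 6- and 12-month effects from the condition-by-Followup terms. This alone brought the bias to 0 and rejection to 5% in every scenario run, and it makes the global null match its description.

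Optionally, constrain β8 to zero, since baseline precedes the intervention. The global null then becomes β9 = β10 = β11 = 0 with 3 df. This is not a substitute for the interaction: on its own it leaves a bias of 0.09 SD at g = 0.05 SD.

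To make the comparison with Model A cleaner still, use matching random effects and fit Model C to Model A's completers as well as to all patients.

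The cost is SAP wording and precision in a secondary model; no new data are needed. The SE of β11 rises from 0.056 to 0.079 SD (0.075 with β8 = 0) at correlation 0.7 without a patient slope, close to Model A's 0.08. With slope variance 0.5 it rises from 0.076 to 0.108.
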